12.1.2. Classification of Causal Relationships

For each reported AE, the causal relationship between the AE and the study device (for VenaSeal™ and ETA treatment only) and index-procedure will be classified as not related, unlikely, possible, probable or causal relationship (**Table 11**).

Table 11: Causality Assessment

Not related	
Relationship to the device or procedures can be excluded when:
 
the event is not a known side effect of the product category the device belongs to or of similar devices and procedures;the event has no temporal relationship with the use of the investigational device or the procedures;the serious event does not follow a known response pattern to the medical device (if the response pattern is previously known) and is biologically implausible;the discontinuation of medical device application or the reduction of the level of activation/exposure - when clinically feasible – and reintroduction of its use (or increase of the level of activation/exposure), do not impact on the serious event;the event involves a body-site or an organ not expected to be affected by the device or procedure;the serious event can be attributed to another cause (e.g. an underlying or concurrent illness/ clinical condition, an effect of another device, drug, treatment or other risk factors);
-------------	--

	
 the event does not depend on a false result given by the investigational device used for diagnosis, when applicable; harms to the subject are not clearly due to use error; 
In order to establish the non-relatedness, not all the criteria listed above might be met at the same time, depending on the type of device/procedures and the serious event.

Unlikely	The relationship with the use of the device seems not relevant and/or the event can be reasonably explained by another cause, but additional information may be obtained.
Possible	The relationship with the use of the investigational device is weak but cannot be ruled out completely. Alternative causes are also possible (e.g., an underlying or concurrent illness/ clinical condition or/and an effect of another device, drug or treatment). Cases were relatedness cannot be assessed or no information has been obtained should also be classified as possible.
Probable	The relationship with the use of the investigational device seems relevant and/or the event cannot reasonably be explained by another cause, but additional information may be obtained.
Causal relationship	
The event is associated with the investigational device or with procedures beyond reasonable doubt when:
 
 the event is a known side effect of the product category the device belongs to or of similar devices and procedures; the event has a temporal relationship with investigational device use/application or procedures; 
 the event involves a body-site or organ that 
 the investigational device or procedures are applied to; the investigational device or procedures have an effect on; the serious event follows a known response pattern to the medical device (if the response pattern is previously known); the discontinuation of medical device application (or reduction of the level of activation/exposure) and reintroduction of its use (or increase of the level of activation/exposure), impact on the serious event (when clinically feasible); other possible causes (e.g. an underlying or concurrent illness/clinical condition or/and an effect of another device, drug or treatment) have been adequately ruled out; harm to the subject is due to error in use;

- the event depends on a false result given by the investigational device used for diagnosis, when applicable;

In order to establish the relatedness, not all the criteria listed above might be met at the same time, depending on the type of device/procedures and the serious event.

The following definitions (**Table 12**) are intended as guidelines for classifying causal relationships between the event and the VenaSeal™ or ETA system and the index- procedure (Timeframe for assessing implant procedure relationships begins when subject is being prepared for the procedure).

Table 12: Adverse Event Relationship Definitions

Related to	Definition
Procedure with the VenaSeal™ closure system, ETA, or surgical stripping (procedure relatedness)	Any AE that occurs within 30 days of the index procedure unless specifically shown not to be related to that procedure.
VenaSeal™ closure system (product relatedness)	Any AE involving the function of the product, or the presence of the product in the body. Included in this category are events that are directly attributed to the product.
ETA devices (product relatedness)	Any AE involving the function of the laser or RF generator used in a treatment with the ETA arm. Included in this category are events that are directly attributed to the product.

12.2. Foreseeable Adverse Events and Foreseeable Adverse Device Effects

A list of adverse events or complications associated with the use of the applicable devices that may occur or require intervention can be found in the applicable IFU. These expected events are considered anticipated adverse events that can be predicted to occur with some frequency, irrespective of how low that frequency is expected to be. For the list of anticipated AEs and anticipated adverse device effects associated with the treatments in this study refer to the applicable IFUs.

Medtronic Business Restricted

CONFIDENTIAL

056-F275, v B Clinical Investigation Plan Template

Medical occurrences that are inherent to an intervention and expected to occur in the majority of subjects for a projected duration may be considered unavoidable. Such events include those listed in **Table 13**. These medical occurrences should not be reported as AEs during this study.

12.3. Recording and Reporting of Adverse Events

Events will be recorded on the appropriate CRFs entering information as documented in the subject's medical records. Events will be reported throughout the course of study (from the moment the index procedure is initiated until completion of follow up or exit). Due to the post market nature of this study, only adverse events meeting the below criteria will be reported).

1. All AEs occurring in the target limb, including but not limited to the following specific events:
 - Hypersensitivity
 - Phlebitis
 - Granuloma
 - Endovenous glue induced thrombosis (EGIT) or endovenous heat induced thrombosis (EHIT)
 - Symptomatic DVT.
2. Symptomatic PEs
3. Serious adverse events (SAE)
4. Non-subject (users) adverse events: AEs occurring to the users or other site personnel related to the device or the procedure.

For all reportable AEs, investigators should assess and record at least the following information on the AE CRF:

1. Date the event started (if full date is not available, partial date is allowed)
2. Date site became aware of event
3. Date event first determined to be a Serious Adverse Event, if applicable
4. Event term
5. Event description
6. Action taken/treatment
7. Which seriousness criteria did the event meet, if applicable
8. Relationship of the event to the procedure
9. Relationship of the event to the device (for VenaSeal™ and ETA treatment only)
10. Narrative (describe any additional details relevant to the AE)
11. Outcome of the event.

Events described in **Table 13** are considered unavoidable events inherent to surgical procedure that is expected to occur in all subjects for a projected duration according to the Investigator's opinion. Unavoidable events should not be reported unless the event worsens or is present outside the stated timeframe from the index procedure.

Table 13: Expected and Unavoidable not to be reported adverse events

Event Description	Timeframe from the procedure
Anesthesia related nausea/vomiting	24 hours
Low-grade fever (<100°F or <37.8°C)	48 hours
Incisional pain (with or without standard treatment and patient not returning to clinic to have additional treatment)	72 hours
Mild to moderate bruising / ecchymosis *	7 days
Back pain related to laying on table	72 hours

Bleeding at access site (not requiring treatment)	24 hours
Emergency room visits and procedures not meeting the SAE definition**	NA

* Ecchymosis events will not be considered AEs unless they are classified as significant by the Investigator due to the more serious nature of it.

**Emergency room visits and procedures will not be considered collectable AEs unless there is a potential relationship with the VenaSeal™ system.

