| | 
• Endovenous glue induced thrombosis (EGIT) or endovenous heat induced thrombosis (EHIT)• Symptomatic deep vein thrombosis (DVT) events 
7. Additional events evaluated through 60 months (through 12 months for VenaSeal vs. Surgical Stripping Study)
 
• Symptomatic Pulmonary embolism (PE)• Serious adverse events (SAEs) 
Healthcare utilization secondary endpoints
 
8. Number and type of adjunctive treatments conducted through 12 months post-index procedure.9. Healthcare utilization related to the target limb VRD, as determined by the number of healthcare visits conducted, and other health-related resources utilized (e.g., home healthcare services) between study visits through 60 months (through 12 months for VenaSeal vs. Surgical Stripping Study).10. Procedures, tests and treatment of AEs related to the treatment modality or index procedure through 60 months (through 12 months for VenaSeal vs. Surgical Stripping Study).11. VLU Study: Healthcare utilization and routine wound care treatments between study visits through 60 months. 
Patient Experience secondary endpoints
 
12. Time to return to normal activities as reported by the patients.13. Intra-procedural and post-procedural pain at the index procedure, and pain at 7 and 30 days as reported by the patient using the numeric rating scale (NRS) with a scale of 0-10.14. Change in venous disease symptoms at 7 and 30 days, and at 6, 12, 24, 36, 48, and 60 months compared to baseline (7 and 30 days, 6 and 12 months only for VenaSeal vs. Surgical Stripping Study), as measured by the revised Venous Clinical Severity Score (rVCSS) and subject self-reporting.15. Change in AVVQ score at 30 days, and 6, 12, 24, 36, 48, and 60 months (30 days, 6 and 12 months only for VenaSeal vs. Surgical Stripping Study) compared to baseline.16. Change in EuroQoL Group 5-Dimension Self-Report Questionnaire (EQ-5D-5L) at 30 days, and 6, 12, 24, 36, 48 and 60 months (30 days, 6 and 12 months only for VenaSeal vs. Surgical Stripping Study) compared to baseline. |
|--|--|

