- Subject's healthcare utilization related to their target limb VRD, as determined by medical record review and/or subject's report of healthcare visits conducted and other health-related resources utilized (e.g. home healthcare services) between study visits.
- Procedures, tests and treatment of AEs related to the VenaSeal™ system or the index procedure, as reported by sites in AE reporting.
- VLU Study: Subject's healthcare utilization and routine wound care treatments between follow-up visits through 60 months.

VLU Assessment on the target limb

Patients who enter the study at designated VLU sites with an active VLU (CEAP 6) on the target limb will receive wound care and compression therapy per the site's standard of care for their VLUs, and undergo ulcer assessments at screening, baseline and each follow-up visit until the ulcer is healed.

At the Screening visit, after consent has been obtained, target limb ulceration will be photographed by the provided eKare imaging equipment to assess etiology and if circumferential. Any ulcer curvature around the leg that extends out of sight and that cannot be captured in a single photograph would be considered as a circumferential ulcer and such subjects will not be included in the study. These photographs captured as part of routine care within 60 days can also be utilized, as deemed appropriate by the treating physician. Photographs will be submitted to the core laboratory to assess venous etiology within 3 business days. If the core laboratory concludes that the ulcer is of non-venous etiology, then the subject will be considered as a screen failure and exited from the study. The baseline ulceration

Medtronic Business Restricted

CONFIDENTIAL

056-F275, v B Clinical Investigation Plan Template

photographs must be taken within 7 days of the index procedure. If the baseline visit is scheduled more than 7 days from the index procedure, the site may collect all remaining baseline data and hold off on taking the photographs until the day of the index procedure, prior to the start of the procedure. The baseline photographs will be sent to the core laboratory for assessments.

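### The Table 13 footnote makes non-serious emergency-room visits collectable as AEs only for a potential VenaSeal relationship, so the exception differs by arm and conflicts with the target-limb rule in Protocol 12.3

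*Protocol*

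**What the plan says.** Protocol 12.3 first lists what is reportable. Criterion 1 is "All AEs occurring in the target limb, including but not limited to the following specific events"; criteria 2 to 4 add symptomatic PEs, SAEs, and device- or procedure-related events in users. None of these depends on the arm.

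Table 13 then lists expected, unavoidable events that are not to be reported. One row is "Emergency room visits and procedures not meeting the SAE definition", with the time frame given as NA. Its footnote reads: "Emergency room visits and procedures will not be considered collectable AEs unless there is a potential relationship with the VenaSeal™ system". The general release for Table 13 is: "Unavoidable events should not be reported unless the event worsens or is present outside the stated timeframe from the index procedure".

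Protocol 12.1.2 has relatedness categories for every arm. Table 12 defines procedure relatedness for VenaSeal, ETA and stripping together, and it has a separate ETA device category: "Any AE involving the function of the laser or RF generator used in a treatment with the ETA arm". The footnote uses neither.

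Secondary endpoint 10 (Synopsis) covers "Procedures, tests and treatment of AEs related to the treatment modality or index procedure through 60 months". The matching data-collection item in Protocol 10.5, repeated in substance in SAP 7.11 item 3, is narrower: "Procedures, tests and treatment of AEs related to the VenaSeal™ system or the index procedure, as reported by sites in AE reporting".

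**The concern.** Both randomised studies are unblinded (Protocol 6), so whoever applies the exception knows which treatment was given. Table 11 in Protocol 12.1.2 also tells sites to classify a relationship that cannot be assessed as possible, which widens an exception that exists for one arm only. SAP 7.10 tabulates AEs by arm, severity, type and relatedness, and readers will compare the arms. If one arm has a route into the AE log that the other lacks, the counts are not like for like before any analysis starts. The Clinical Events Committee cannot repair this, because it adjudicates events that investigators report (Protocol 13.1). Endpoint 10 is analysed as a listing per recorded AE (SAP 7.9.1.6 item 3), so care for an unrecorded event does not appear there.

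**Working it through.** The plan gives no figure to reproduce and no arithmetic applies. The check is to apply each rule to the same kind of event.

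**Step 1: do the releases reach the ER row?** The time-frame release cannot operate, because the row has no time frame. The worsening release is open to every arm, although it suits a symptom better than a visit. The footnote is the only exception written for this row.

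**Step 2: apply the footnote and criterion 1 to a non-serious target-limb event seen in the ER.**

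| Arm (treated as randomised) and relationship | Table 13 footnote alone | Criterion 1 alone |
|---|---|---|
| VenaSeal, potential relationship with VenaSeal | collectable | reportable |
| VenaSeal, no such relationship | not collectable | reportable |
| ETA, potential relationship with the ETA device or procedure | not collectable | reportable |
| Stripping, potential relationship with the procedure | not collectable | reportable |

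The footnote column depends on the arm; the criterion 1 column does not. They agree only in the first row.

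**Step 3: is precedence stated?** No. Table 13 clearly does act as a carve-out from criterion 1 elsewhere, since it removes early bruising and minor access-site bleeding, both target-limb events. A site could reasonably follow either rule for an ER case.

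**Step 4: does the row fit the table?** Protocol 12.2 describes these events as inherent to an intervention and expected in most subjects; 12.3 says all subjects. An ER visit is neither. It is also an action taken, whereas an AE is the underlying condition.

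**Step 5: which outputs are exposed?** They are the by-arm AE counts in SAP 7.10 and the endpoint 10 listing. SAP 7.9.1.5 states no formal hypothesis test for the target-limb AE endpoint or for the SAE, DVT and PE endpoint. ER visits related to venous reflux disease are counted by arm under utilization whether or not an AE is recorded (SAP 7.9.1.6 item 2), so that rate is unaffected.

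**Step 6: compare the utilization wording.** Protocol 10.5 and SAP 7.11 item 3 name VenaSeal or the index procedure. Endpoint 10 names the treatment modality or the index procedure. Procedure relatedness covers all three treatments and is presumed for any AE within 30 days unless shown otherwise. The remaining gap is comparator-device-related events that are not attributed to the procedure.

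**The case against.** The strongest reply is that the row concerns a care setting, not an event. On that reading, an ETA or stripping subject with target-limb phlebitis is reportable under criterion 1 wherever treated, and the ER row removes only the visit itself. The worsening release adds a route in every arm. Protocol 15.1 openly limits AE scope because the study is post-market and has no primary safety endpoint. The adjudicated events are named items in all studies, and any distortion would count against the sponsor's device.

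Much of this stands. A reader might infer that comparator ER events are never collected, or that the same target-limb event is cleanly excluded in one arm. The documents do not support that: criterion 1 calls for those events in every arm, so the text contradicts itself and does not plainly exclude them. A reader might also take the wording in Protocol 10.5 and SAP 7.11 as VenaSeal-only. It is not, because both add the index procedure.

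The reply does not explain why the exception names one treatment when arm-neutral terms were available, and it does not supply the missing precedence rule. If the row removes only the visit, the footnote has no purpose. A direction against VenaSeal does not make the counts comparable.

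**Conclusion.** The point holds as an arm-dependent exception and an unresolved conflict within Protocol 12.3. It affects descriptive safety tables and one listing; no hypothesis test, alpha allocation, power or sample size changes. The likely direction is to add AEs to the VenaSeal arm, provided that sites follow the footnote and subjects are treated as randomised.

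The size cannot be derived from the documents. A reader might assume that 2% to 5% of subjects have a treatment-related, non-serious target-limb event handled in the ER. With 264 / 2 = 132 per arm in the ETA study, that is 132 × 0.02 = 2.6 to 132 × 0.05 = 6.6 subjects. With 108 / 2 = 54 in the stripping study, it is 54 × 0.02 = 1.1 to 54 × 0.05 = 2.7. These are not estimates of the bias. The rate is an assumption, and a loss of that size needs the footnote to override criterion 1 completely in the comparator arm. If criterion 1 prevails, the difference for these events is zero.

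**What to change.** Preferred: delete the ER row and its footnote from Table 13. The underlying condition is then reportable or not under criteria 1 to 4, in the same way in every arm.

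Alternative: keep the row, but reword the exception to *a potential relationship with the assigned study treatment (VenaSeal, ETA or surgical stripping) or the index procedure*, and state that criterion 1 prevails over Table 13.

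In either case, reconcile ER visits already recorded under healthcare utilization with the AE log in all arms, and query those with no AE entry. This recovers only visits related to venous reflux disease of the target limb, because that is what the utilization form covers.

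As a minor alignment, change the wording in Protocol 10.5 and SAP 7.11 item 3 to *treatment modality or index procedure*, to match endpoint 10.

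The cost is one table edit, two wording changes, one reconciliation, and a few more AE forms and queries.

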12.4. Recording and Reporting of Device Deficiencies

Device deficiency information will be collected and recorded throughout the study. The Device Deficiencies related to the VenaSeal™ system and Medtronic ClosureFast™ system (ETA treatment modality) will need to be reported in the CRF.

- Device deficiencies that lead to an AE by study definition will be reported on the AE CRF only.
- Device deficiencies that did not lead to an AE will be reported on a Device Deficiency CRF (one for each device deficiency).
- Device deficiencies that did not lead to an AE but might have led to a SADE if
 - a suitable action had not been taken, or
 - an intervention had not been made, or
 - circumstances had been less fortunate, should be reported to Medtronic on a Device Deficiency CRF.
- Device deficiencies that did not meet any of the above criteria will be reported to Medtronic through normal complaint process.

The Device Deficiencies related to any other products used in the study should be reported per site's standard practice of reporting to their manufacturer. This reporting requirement is a deviation from ISO 14155:2020 due to the post-market nature of the study.

It is the responsibility of the investigator to report all product complaint(s) associated with a medical device distributed by Medtronic, regardless whether they are related to intended use, misuse or abuse of the product. In addition to study requirements outlined above, additional reporting of product complaints by the site must be done according to the local Standard Operating Procedures. Medtronic will notify the Regulatory Authority (e.g., CA) as applicable for the following incidents immediately upon learning of them and is not limited to AEs and DDs only:

*Medtronic Business Restricted***CONFIDENTIAL**

056-F275, v B Clinical Investigation Plan Template

- Any malfunction or deterioration in the characteristics and/or performance of a device, as well as any inadequacy in the labeling or instructions for use which led or might have led to the death or serious deterioration in the state of health of a patient, user, or other person.
- Any technical or medical reason resulting in withdrawal of a device from the market by the manufacturer.
- Any serious deterioration in the state of health, including:
 - Life-threatening illness or injury.
 - Permanent impairment of a body function or permanent damage to a body structure.
 - A condition necessitating medical or surgical intervention to prevent permanent impairment of a body function or permanent damage to a body structure.

12.5. Adverse Event and Device Deficiency Review Process

AEs/Device Deficiencies will be reviewed by Medtronic Study Management and/ or designee. This review will include the determination whether the AE/Device Deficiency meets regulatory reporting requirements. The sponsor will ensure timely AE/Device Deficiency reporting to meet global and country specific regulatory requirements.

12.6. Reporting of Adverse Events

The information below outlines the AE reporting requirements from the investigator to Medtronic (**Table 14**). Investigators and Medtronic are obligated to report AEs to their EC/IRB in accordance with the requirements and local regulations. Refer to section 12.3 and section 12.4 for a list of types of AEs that are required to be reported during the study.

Table 14: Investigator reporting requirements

Timeframe for Reporting	Event Type
Immediately, but no later than 3 calendar days of the investigator's / site's first knowledge of the event (or sooner if required by local regulation)	
• Adverse Device Effect (ADE) or Device Related Adverse Event. Device Deficiency (DD).• Device Deficiency that might have led to a SADE• Serious Adverse Device Effect (SADE)• Serious Adverse Event (SAE)
In a timely manner from the investigator's / site's first knowledge of the event	Adverse Event (AE): only those that are required to be reported according to CIP.

